### **8.1.2      *Evaluation of SRI(X)***

In addition to BICLA, a novel endpoint, the SLE Responder Index [SRI] with a modification used as a primary endpoint in the Anifrolumab study, the results of which were presented and published as an abstract at the American College of Rheumatology (ACR) National Meeting in November, 2015. The basic difference between the SRI defined in our protocol and the SRI in the Anifrolumab study is the addition of a fourth component of the endpoint. The original definition of SRI in the protocol does not include the fourth component based on the use of restricted medications.

The use of restricted medications is an important confounding factor when we analyze the endpoints such as BICLA, and SRI(X). Hence an additional component based on the use of restricted medications (same as the 4th component in the definition of BICLA) is deemed necessary to incorporate into the original definition of SRI (X) in the protocol. The modification to the existing definition of SRI is described below.

An SRI(X) [X= 4, 5, 6, and 8] response @ Day T (e.g. T = 85, 169) is defined as:

- a reduction in Day 1 SLEDAI-2K disease activity score of  $\geq X$  points at Day T; and,
- no worsening of disease (defined as an increase of  $\geq 10$ mm on a 100mm VAS from Day 1 as measured by the MDGA up to time T; and,
- no new BILAG-2004 Index 'A' organ system score and no more than one new or worsening BILAG-2004 Index 'B' organ system scores up to time T ; and,
- *No changes in concomitant medications according to the following criteria:*
  - No increase of or addition of a new immunosuppressant agent (azathioprine, methotrexate, anti-malarial) over baseline levels
  - No increase in corticosteroid dose above baseline level outside of those allowed per protocol.

If a subject failed any of the above criteria, the SRI(X) response status of the subjects will be set to non-responder.

For the determination of missing SRI(X) response status, all subjects who prematurely discontinue from the study medication will be imputed as a non-responder at all scheduled efficacy visits subsequent to the point of discontinuation.

If any subject has at most one missing component (e.g. MDGA for SRI(X)) at a given efficacy visit not due to premature discontinuation, the component-wise response status will be imputed based on the following rules.

- If the given visit is not the last scheduled efficacy visit (Day 169), imputation will depend on the observed responses from the immediate previous efficacy visit and the immediate next efficacy visit within 28 days of the current visit date.
- If the given visit is the last scheduled efficacy visit (Day 169), the imputation will depend on the observed responses at the previous 2 consecutive efficacy visits (within 56 days).
- If a subject has response (at component level) at both efficacy visits, the missing response status at current visit will be imputed as responder. Otherwise, response status will be set to non-responder.

The SRI(X) response status (composite) for a subject who has more than one component (e.g. MDGA and SLEDAI-2K are missing for SRI(X)) missing at a given (efficacy) visit not due to premature discontinuation will be imputed as non-responder.

After any imputation above or none, if for some reason the SRI(X) response status still cannot be determined, including the case where baseline data is missing, then its value will be set to non-responder.

Note that, the corrected threshold is 10mm in the second component of SRI(X) instead of 30mm (as in the original protocol) on a 100mm VAS of MDGA. The correct threshold is used in the definition of SRI(X) in this section.

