4.5.3 Corticosteroids (Prednisone or Prednisone Equivalent) Dosing

- Prior to Randomization: Corticosteroids (prednisone or prednisone equivalent; refer to Appendix 1) may be used in accordance with the Investigator's clinical judgment and best standard of care. A maximum daily dose of 30mg/day is acceptable to be eligible for the

study and start screening; however, daily dose must be tapered down to a maximum of 10mg/day for at least 5 days prior to Day 1 (randomization day).

- Study Day 1 (randomization day): subjects requiring the use of prednisone (or prednisone equivalent) will be on a maximum dose of 10mg/day.
- Post Day 1 (after initiation of study therapy):
 - For subjects who flare or need to increase their prednisone (or prednisone equivalent) to control disease activity a one-time increase of up to a maximum daily dose of 20 mg/day for up to 2 consecutive days will be allowed to transiently manage disease activity.
 - A subject who requires a total daily dose of prednisone (or prednisone equivalent) exceeding 20 mg/day or who has another flare after the first rescue therapy, will be considered a treatment failure.
 - A subject who meets the treatment failure criteria as described above may continue on study medication; however, a subject requiring more than 20 mg/day of prednisone (or prednisone equivalent) for more than 7 days in the short-term period, or more than 14 days in the long-term extension period, will be discontinued.

Tapering of steroids during the course of the study is encouraged and should be evaluated at all visits. Once subject has received the first dose of study drug, prednisone (or prednisone-equivalent) may be tapered down at the discretion of the Investigator.

4.5.4 *Rescue Therapy*

4.5.4.1 *Short- Term Period*

A one-time increase of up to a maximum daily dose of 20 mg/day for up to 2 consecutive days will be allowed to transiently manage disease activity and will not be considered a treatment failure.

- A subject who requires a total daily dose of prednisone (or prednisone equivalent) exceeding 20 mg/day or who has another flare after the first rescue therapy, will be considered a treatment failure.
- A subject who meets the treatment failure criteria based on prednisone use may continue on study medication; however, a subject requiring more than 20 mg/day of prednisone (or prednisone equivalent) for more than 7 days in the short-term period, will be discontinued.

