### 4.2 Secondary Efficacy Endpoint(s)

- Proportion of subjects who meet response criteria for the SLE Responder Index(4) [SRI(4)], SRI(5), SRI(6), and SRI(8) at Day 169
- Proportion of subjects who meet response criteria for the SLE Responder Index(4) [SRI(4)], SRI(5), SRI(6), and SRI(8) at Day 85
- Proportion of subjects with BICLA response at Day 85
- Change from baseline in CLASI score at Day 85 and Day 169

- Percentage of subjects with an improvement of at least 4 or an improvement of at least 50% from baseline in their CLASI score at Day 85 and Day 169
- Proportion of subjects with an improvement of at least 4 or an improvement of at least 20% from baseline in their CLASI score at Day 85 and Day 169
- Change from baseline in arthritis, as assessed by American College of Rheumatology (ACR) 28 joint counts of tender, swollen, and as well as active joints, i.e. those that are both tender and swollen at Day 85 and at Day 169
- The change from baseline in the following other indices SLE activity over time:
  - ◆ The overall BILAG-2004 score
  - ◆ The overall SLEDAI-2K score
  - ◆ The overall MDGA (Physician's Global Assessment of Disease Activity) score
- Change from baseline in SLICC/ACR Damage Index
- The cumulative corticosteroid and immunosuppressant use over time

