#### 5 SAMPLE SIZE AND POWER

The sample size calculation is based on power to compare the proportion of subjects who achieve BICLA response (the BICLA response rate) at Day 169 between each BMS-931699 dose arm and the placebo arm. With a one-sided continuity corrected chi-squared test at significance level 0.05, data from 70 treated subjects per arm will provide at least 89% power to detect a 25% increase in the BICLA response rate in the active treatment arm (i.e.. 50% response rate in BMS active arm) compared to placebo and provide 74% power to detect 20% increase in the BICLA response rate in the active treatment arm (i.e., 45% response rate in BMS-931699 arm) compared to placebo, assuming that the placebo arm has 25% response rate which is reasonable based on the EMBLEM phase 2 trial result. No adjustment will be made for multiplicity.

The primary efficacy analysis will be conducted on all randomized patients who received at least one dose of the study drug. In order to get 70 treated subjects per arm, an adequate numbers of subjects need to meet the inclusion/exclusion criteria at screening.

If the interim analysis for futility and dose adaptation suggests an additional dose arm at a lower dose level needs to be added, then up to 40 additional subjects may be randomized.

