### **8.3 Missing Measurements**

For listings of binary response efficacy variables, missing values will be presented as missing. For determination of binary response variables, handling of missing values for BICLA and SRI(X) responses is addressed in [Sections 8.1.1](#) and [8.1.2](#) unless otherwise specified.

If the response cannot be assessed due to missing data or a subject's early discontinuation, the following conventions will be implemented in a sequence:

- Any subject who prematurely discontinues the trial during the Short-term period after receiving study medication will have data imputed as non-responder at all scheduled protocol visits subsequent to the point of discontinuation up to the end of the Short-term period.
- After any imputation above or none, if for some reason the binary variable still cannot be determined, including the case where baseline data is missing, then its value will be set to non-responder.

For the analysis of continuous efficacy variables, mixed model will be used based on assumption of data being missing at random. Subjects with only baseline observations will be excluded from any changes from baseline analyses.

For safety, PK and immunogenicity measures and biomarkers, missing values will not be imputed.

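### CLASI response and the continuous secondary endpoints have no stated rule for values after a disqualifying medication change on study drug, although the SAP calls such medication a confounder and counts it as non-response in BICLA and SRI(X)

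*SAP*

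**What the plan says.** SAP 8.1.2 explains why SRI(X) was modified: "The use of restricted medications is an important confounding factor when we analyze the endpoints such as BICLA, and SRI(X". It adds to SRI(X) the medication component already in BICLA (SAP 8.1.1). A new or increased immunosuppressant, or a steroid increase beyond what the protocol allows, makes the subject a non-responder.

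The other secondary efficacy endpoints are treated differently:

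- **CLASI response.** SAP 4.2 has two versions, both defined on score change alone. One reads "Percentage of subjects with an improvement of at least 4 or an improvement of at least 50% from baseline in their CLASI score"; the other replaces 50% with 20%.
- **Continuous endpoints.** SAP 7.1 and 7.5.2 fit a repeated-measures mixed model to CLASI, BILAG-2004, SLEDAI-2K, MDGA and ACR28. The only handling rule concerns missing data. SAP 8.3 says: "For the analysis of continuous efficacy variables, mixed model will be used based on assumption of data being missing at random".

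Such values will exist. Protocol 4.5.3 says: "A subject who meets the treatment failure criteria as described above may continue on study medication". Failure there means needing more than 20 mg/day of prednisone equivalent, or a further flare after the first rescue.

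**The concern.** Added steroid or immunosuppressant can improve a SLEDAI-2K total, a joint count or a skin score, just as it can improve a composite built from them. Under the plan, a subject with a disqualifying change can be an SRI(4) non-responder at a visit because of that change. The improved SLEDAI-2K from the same visit then enters the arm mean as benefit.

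If this happens more often on placebo, the active-minus-placebo difference shrinks on CLASI response and on the continuous endpoints. Those results could then disagree with BICLA and SRI(X) only because medication is handled differently, and no planned efficacy analysis would separate that explanation from a real difference between endpoints.

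**Working it through.** **1. The plan's own figure.** The only stated power is for BICLA (SAP 5). It rests on a one-sided chi-square test with continuity correction at the 0.05 level and a placebo rate of 25%. For the larger effect the SAP claims: "data from 70 treated subjects per arm will provide at least 89% power to detect a 25% increase in the BICLA response rate". For the smaller effect the claim is: "provide 74% power to detect 20% increase in the BICLA response rate". Inverting the continuity correction gives an effective size n0 = (n·d − 1)² / (n·d²), with n = 70.

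- d = 0.25: (17.5 − 1)² / 4.375 = 62.2, power 89.95% (stated: at least 89%).
- d = 0.20: (14 − 1)² / 2.8 = 60.4, power 74.97% (stated: 74%).

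Both reproduce. BICLA already contains the medication component, so this point does not touch that calculation.

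**2. Does another section close the gap?**

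- SAP 8.3 makes premature discontinuers non-responders on binary endpoints. That covers CLASI response after discontinuation, but not a medication failure in someone still on drug.
- SAP 8.5 keeps efficacy assessments made within 28 days of the last dose.
- SAP 7.5.4 adds stratum adjustment for the primary endpoint and, conditionally, an analysis excluding some discontinuers. SAP 7.5.5 is per-protocol. Both stop at the primary endpoint and SRI(4)/SRI(6).
- SAP Appendix 1 lists no post-baseline medication deviation.
- SAP 7.11.2 defines treatment failure, but only for a time-to-event analysis.
- SAP 7.4.5 and 7.4.6 summarise medication use without linking it to efficacy values.

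Nothing in the visible text closes it.

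**3. Size, on assumptions only.** The documents give no rate of non-allowed medication. Let f be the proportion with a disqualifying change who are still counted (P placebo, A active), r the share of them who then meet the CLASI threshold, and g the SLEDAI-2K gain per user. With r and g equal across arms:

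- shift in the CLASI response difference = (f_P − f_A) × r
- shift in the SLEDAI-2K mean difference = (f_P − f_A) × g

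| Assumed use, placebo v active | r | CLASI shift | g | SLEDAI-2K shift |
|---|---|---|---|---|
| 15% v 15% | 0.5 | 0 | 4 | 0 |
| 15% v 10% | 0.4 | 2 points | 3 | 0.15 |
| 20% v 10% | 0.5 | 5 points | 4 | 0.4 |
| 30% v 15% | 0.5 | 7.5 points | 4 | 0.6 |

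These lean high. Some users will discontinue and are already CLASI non-responders, and applying the full gain to every user has no support in the documents. If use were higher on active, the shift would reverse.

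**4. Scale.** Borrow 25% v 45% from the BICLA planning as a stand-in for CLASI response with medication failures counted as non-response. At 20% v 10% use and r = 0.5, the analysed rates become 25 + 10 = 35% and 45 + 5 = 50%, a difference of 15 instead of 20 points. The 90% interval half-width with 70 per arm is 1.645 × √(0.35×0.65/70 + 0.50×0.50/70) = 13.6 points, so a 5-point shift is a little over a third of it. In standardised terms, a 0.5 SD difference becomes 0.5 − 0.10×0.5 = 0.45 SD or 0.5 − 0.10×1.0 = 0.40 SD if the added medication is worth 0.5 or 1.0 SD.

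**The case against.** The case against is substantial, and most of it limits the point.

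- **Allowed rescue is outside it.** A reader might infer that any rescue on placebo hides a drug effect. The documents do not support that. The one-time increase permitted in Protocol 4.5.4.1 is not a treatment failure, and BICLA and SRI(X) both tolerate it. Only non-allowed medication separates the endpoints.
- **Some failures leave study drug.** Protocol 3.5 requires discontinuation when new manifestations need medication the protocol does not approve, and beyond stated prednisone limits. That shrinks the exposed group but does not empty it, since a second flare is a failure under Protocol 4.5.3 and the subject may continue.
- **Using every observed value is a legitimate estimand.** A reader might infer that the planned models are wrong, or that the protocol's CLASI endpoint must be redefined. Neither follows. SAP 8.1.2 speaks of endpoints such as BICLA and SRI(X), and extending its reasoning to a skin score or joint count is an inference. What stands is that the SAP does not state its choice for these endpoints; that all values are used is itself read from the absence of a rule.
- **Consequences are limited.** These endpoints get 90% intervals without p-values. Unequal medication use would show in the steroid summaries, the reasons for BICLA non-response and the time to treatment failure.
- **Futility.** A reader might infer that dose arms could be dropped because of this. The 0.2 threshold applies to the BICLA predictive probability. ACR28 is one of several supporting inputs (SAP 7.10.2), under a separate interim plan not available here.
- **Redaction.** Protocol 3.4.1 and SAP 7.11.1 and 7.11.3 cannot be read, so further management rules or analyses may exist there.

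**Conclusion.** The gap holds in a limited form. BICLA and SRI(X) count a disqualifying medication change as non-response. CLASI response and the five mixed-model measures have no stated rule for values after such a change in subjects who remain on drug.

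Whether this biases anything is unknown. It needs more non-allowed medication on placebo than on active and a benefit from it. With equal use and benefit the shift is zero. At an assumed 20% v 10% use it is about 5 CLASI points or 0.4 SLEDAI-2K points, as an upper-side figure.

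The primary endpoint and its power are unaffected. This is an inexpensive improvement to consider for interpreting secondary results, not a flaw that undermines the trial.

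**What to change.** Keep the planned analyses and add to SAP 7.5.2 and 7.5.4, each shown beside its planned counterpart:

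1. A supplementary analysis of both CLASI responder endpoints in which a subject who fails the BICLA/SRI(X) medication component is a non-responder.
2. A supplementary mixed model for CLASI, BILAG-2004, SLEDAI-2K, MDGA and ACR28 with values after the first BICLA-defeating medication change set to missing.

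Two reconciliations come first:

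- **The drug list.** The BICLA definition in Protocol 1.3.1 includes mycophenolate and leflunomide; SAP 8.1.1 and 8.1.2 name only azathioprine, methotrexate and antimalarials. Reusing the flag as it stands would carry that discrepancy over.
- **Who stays on drug.** Protocol 3.5 joins the 20 mg and 7-day limits with and/or, whereas Protocol 4.5.3 and 4.5.4.1 discontinue only when more than 20 mg/day is needed for more than 7 days. These passages must be made to agree.

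The cost is SAP text and reuse of a flag already needed for BICLA and SRI(X). The downsides are slightly lower CLASI response rates in the supplementary analysis, and reliance on missing at random for subjects with disqualifying medication.

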### ***8.1.3 Evaluation of Major Clinical Response and Partial Clinical Response***

Major and Partial Clinical responses are defined as:

- **Major Clinical Response:** a patient with BILAG C scores or better at 6 months with no new BILAG A or BILAG B scores AND maintenance of response with no new BILAG A or B scores between 6 and 12 months.
- **Partial Clinical Response:** a patient with BILAG C scores or better at 6 months with no new BILAG A or BILAG B scores and maintenance of response without a flare for 4 months.

If a subject is not meeting any of the above criteria, the response status will be set to non-responder.

If a subject has any missing data at a particular visit, the subject will be excluded from the analysis at that particular visit. The details will be provided in the LTE SAP.

### ***8.1.4 Evaluation of Flare and Severity of Flare***

Flare and severity of flare based on new BILAG 2004 is defined as follows:

- Severe flare is any BILAG 2004 “A” score in any system due to items that are new or worse.
- Moderate flare is two or more “B” scores that are new or worse.
- Mild flare would be any patient with a single “B” score due to items that are new or worse or in those with three or more “C” scores due to items that are new or worse.
- Anyone without these criteria would be categorized as no flare
- If a subject has any missing data at a particular visit, the subject will be excluded from the analysis at that particular visit.

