3.4.2 *Other Restrictions and Precautions*

Active SLE and its treatment are associated with increased risk of infection. Subjects should be provided information about the signs of the most common serious infections (eg, pneumonia, sepsis) and must have the knowledge and means to access appropriate medical care.

3.5 *Discontinuation of Subjects following any Treatment with Study Drug*

Subjects MUST discontinue investigational product (and non-investigational product at the discretion of the investigator) for any of the following reasons:

- Subject's request to stop study treatment and/or participation in the study
- Any clinical adverse event (AE), laboratory abnormality or intercurrent illness which, in the opinion of the investigator, indicates that continued participation in the study is not in the best interest of the subject
- Termination of the study by Bristol-Myers Squibb (BMS)
- Loss of ability to freely provide consent through imprisonment or involuntarily incarceration for treatment of either a psychiatric or physical (eg, infectious disease) illness
- Unblinding a subject for any reason (emergency or non-emergency)
- Development of new active manifestations of lupus requiring treatment with any non-protocol approved medications during the study.
- Inability or subject's failure to comply with the protocol requirements.
- Subject who misses more than 3 consecutive weekly doses.
- Pregnancy
- Treated with prednisone (or prednisone equivalent) at a total daily dose exceeding 20 mg and/or for more than 7 days (short-term period) or more than 14 days (long-term extension period).

Patients should discontinue from study, perform End of Treatment and Follow-up Day 42 visits, and receive standard of care according to local guidelines.

In the case of pregnancy, the investigator must immediately notify the BMS Medical Monitor/designee of this event. If any female subject becomes pregnant she will be immediately discontinued from the study.

All subjects who discontinue investigational product should comply with protocol specified follow-up procedures as outlined in Section 5. The only exception to this requirement is when a subject withdraws consent for all study procedures including post-treatment study follow-up or loses the ability to consent freely (ie, is imprisoned or involuntarily incarcerated for the treatment of either a psychiatric or physical illness).

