5.4.2 Secondary Efficacy Assessments

5.4.2.1 Short-Term Period

Training and instruction on BILAG 2004 index assessment will be provided and discussed at the Investigator's Meeting or at workshops. The response measure (BILAG) will be reviewed and discussed with the investigational staff at the Investigator Meeting or other forum as a method of standardizing the grading between the investigational staffs. All Investigative site personnel performing BILAG evaluations must be trained and certified.

The BILAG index measures and reports disease activity in different organs/systems separately. The BILAG score is calculated for each of nine systems depending on the clinical features

present and whether they are new, worse, the same or improving in the last 4 weeks compared with previously. A BILAG “A” represents the presence of one or more serious features of lupus. A BILAG “B” represents more moderate features of the disease. A BILAG “C” includes only mild symptomatic features. A BILAG “D” represents only prior activity with no current symptoms due to active lupus. A BILAG “E” represents an organ that has never been involved. Assessments used to determine BILAG score must be performed by the Investigator, or a BILAG certified (an individual who has passed the BMS sponsored BILAG Certification Test) Sub-Investigator. The Sub-Investigator may be a Doctor of Medicine (MD), or someone who is authorized to perform the examinations by training and has been delegated this task by the principal investigator. Changes in therapy based on any clinical or laboratory assessment must be approved by the Investigator or a MD/DO Sub-Investigator.

5.4.2.2 *Long-Term Extension Period*

Secondary efficacy assessments during the long-term extension will be the same as in the short-term period, in order to assess long-term durability of response.

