### **7.11.2 Time to event Analysis**

Time to treatment failure and time to first flare as assessed by new BILAG 2004 index flare definition will be summarized. For those time to event endpoints, if necessary, the point estimate and its 90% confidence interval for the hazard ratio of each active treatment arm versus placebo will be calculated based on the Cox proportional hazards models. In addition, the distribution of time to the occurrence of event will be estimated using Kaplan-Meier method. The analysis will be based on the Efficacy Analysis Population.

Treatment failure is defined as non-protocol treatment i.e., new or increased immunosuppressive treatment or antimalarials; or parenteral corticosteroids; or protocol prohibited dose of oral corticosteroid; or premature discontinuation from study treatment.

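### SAP 8.1.4 drops a recorded BILAG flare whenever anything else is missing at that visit, so time to first flare can lose or delay events that were observed

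*SAP*

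**What the plan says.** SAP 8.1.4 grades flare from BILAG-2004. A severe flare is an A "score in any system due to items that are new or worse". A moderate flare needs two or more new or worse Bs. A mild flare needs one such B, or three or more such Cs. For the rest, "Anyone without these criteria would be categorized as no flare". The last bullet then says: "If a subject has any missing data at a particular visit, the subject will be excluded from the analysis at that particular visit".

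The visible use of this definition is SAP 7.11.2, where "time to first flare as assessed by new BILAG 2004 index flare definition will be summarized" in the Efficacy Analysis Population, by Kaplan-Meier and, if necessary, Cox models. Section 7.11.2 does not say how an excluded visit enters that analysis. For the companion endpoint, time to treatment failure, it does count "premature discontinuation from study treatment" as an event.

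Other endpoints have more specific missing-data rules. For BICLA and SRI(X), SAP 8.1.1 and 8.1.2 impute a single missing component from neighbouring visits and count discontinuation as non-response. SAP 8.3 makes non-response the fallback for binary responses: "if for some reason the binary variable still cannot be determined, including the case where baseline data is missing, then its value will be set" that way.

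**The concern.** Flare is decided by the worst recorded findings, so partial data can be enough. Protocol 5.4.2.1 says: "The BILAG score is calculated for each of nine systems depending on the clinical features". With nine systems, a visit can be incomplete in one and decisive in another. Once a new or worse A is recorded, no value in a missing system could make the visit anything but a severe flare. The last bullet removes the visit all the same.

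What is at stake is the flare analysis only. Events that were observed would not be counted, or would be dated to a later visit. The Kaplan-Meier flare curves would then sit too low, and the hazard ratios would rest on fewer events.

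**Working it through.** **1. Apply the definitions and the last bullet to the same visit.**

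| Recorded scores | Other systems | What the definitions allow | Under the last bullet |
|---|---|---|---|
| One new or worse A | one missing | severe, whatever the missing value | excluded |
| Two new or worse Bs | one missing | moderate or severe | excluded |
| One new or worse B, or three such Cs | one missing | mild or higher | excluded |
| No criterion met | one missing | cannot be determined | excluded |
| Any | none missing | as defined | kept |

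Only in the fourth row is it unknown whether a flare occurred. In the first three a flare is certain, and in the first its grade is certain too.

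**2. Follow the visit into time to first flare.** Suppose a subject has a recorded A at Day 57 with another system missing. If a complete visit at Day 113 shows a flare, the event is dated 113 − 57 = 56 days late. If no later complete visit shows one, the subject contributes no event. The same applies at an End of Treatment visit. BILAG is scheduled there (Protocol Table 5.1-2) and SAP 8.5 keeps assessments within 28 days of the last dose, but 8.1.4 still excludes the visit if it is incomplete.

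**3. Size (illustration only).** The plan gives no flare figure to reproduce. Its power statement concerns BICLA and does not enter here.

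Inputs from the documents:
- 70 subjects per arm (SAP 5)
- 6 post-baseline BILAG visits, at Days 29, 57, 85, 113, 141 and 169

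Assumed inputs:
- severe-flare risk *h* of 3% to 8% per visit
- share *m* of visits with something missing of 2% to 20%, independent of flare

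Subjects with at least one severe flare: E = 70 × [1 − (1 − h)^6].

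- Case A, the first flare is the subject's only one: lost = m × E.
- Case B, the subject stays and can flare again at the same risk: counted = 70 × [1 − (1 − h(1 − m))^6], and lost = E − counted.

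| h | m | E | Lost, case A | Counted, case B | Lost, case B |
|---|---|---|---|---|---|
| 0.03 | 0.02 | 11.7 | 0.2 | 11.5 | 0.2 |
| 0.05 | 0.10 | 18.5 | 1.9 | 16.9 | 1.6 |
| 0.08 | 0.20 | 27.6 | 5.5 | 22.9 | 4.6 |

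(Losses are taken from unrounded values.) In case B, some subjects who are counted have their event dated late.

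**4. Direction.** If *m* is the same in both arms, the counted per-visit risk in case B is h(1 − m) in each arm. The factor (1 − m) cancels from their ratio, so the relative effect is roughly preserved while event counts and absolute differences shrink. Bias in the ratio would need incompleteness that differs between arms. The documents do not say whether it would.

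**The case against.** **The trigger may be narrower than it looks.** SAP 8.1.4 does not say whether missing data means an item, a system grade or the whole BILAG. If it means the whole assessment, no recorded flare is lost. That ambiguity is real, but the word used is any, and a programmer following it would drop partly complete visits.

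**The stakes are low.** Flare is not a primary or listed secondary endpoint, formal testing is limited to BICLA at Day 169 (SAP 7.5), and flare is not named in the futility criteria. This stands. So does the point that a flare at a complete visit is kept, including at an End of Treatment visit within 28 days of the last dose.

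**The contrast with SAP 8.3 is weak.** That section governs binary responses, and flare is a graded endpoint with its own rule. This is fair. The defect lies within 8.1.4 and does not depend on the contrast.

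**A stronger reading is tempting.** A reader might infer that the protocol removes everyone with new lupus activity, so that later flare results describe only those who remained and the treatment difference at Day 169 shrinks. The documents do not support this:
- Protocol 3.5 requires stopping for "Development of new active manifestations of lupus requiring treatment with any non-protocol approved medications during the study", with steroid limits as a separate trigger. That is narrower than any new activity.
- Protocol 4.5.3 and 4.5.4 allow a rescue for flare, and let a subject with another flare after it continue on study medication.
- The visible SAP shows no by-visit flare rate (parts of 7.11 are blacked out). In time to first flare, a flare recorded at a complete visit before departure is already an event.

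**Conclusion.** The point holds in a narrow form. As written, the last bullet of SAP 8.1.4 discards flares that the recorded scores already establish, and the loss or delay carries into time to first flare. This follows from the text and needs no assumed rate.

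The size does not follow from the text. The range of 0.2 to 5.5 subjects per arm rests wholly on the assumed flare and missingness rates, on independence between them, and on reading missing data to include a single missing item or system. The documents do not establish a bias for or against active treatment. The primary analysis is untouched. The correction is still worth making, because the stated rule gives a wrong classification and costs almost nothing to repair.

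**What to change.** Replace the last bullet of SAP 8.1.4 with wording such as:

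> If the recorded scores meet a flare criterion, the visit is classified as at least that grade regardless of missing data in other systems. A visit is treated as missing only if no flare criterion is met by the recorded scores and one or more systems are missing.

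In SAP 7.11.2:
- Count every flare so classified as an event, including one at an End of Treatment visit within 28 days of the last dose.
- Add a supportive analysis in which discontinuation for lack of efficacy or new lupus activity counts as a flare. Time to treatment failure overlaps with this, but it counts discontinuation for any reason and also counts treatment changes.

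The SAP should not instead let a missing system count as showing no new A or B. Together with the default category, that would turn undetermined visits into no flare. A separate crude cumulative proportion is not needed either, because Kaplan-Meier already gives the cumulative estimate.

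The cost is SAP wording and a small programming change, with no new data. One small downside is that a flare visit with a missing system may be graded too low, for example moderate when the missing system would have shown an A. Also, if flare is tabulated by visit, incomplete visits would be kept when they show a flare and not otherwise, so the number of assessable visits should be shown.
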